Schedule B will be initiated after preliminary safety data of AMG 673 in Schedule A (eg, MTD1 is estimated to be $\geq 72 \mu\text{g}$) become available and may be conducted in parallel with Schedule A per Sponsor's decision. For Schedule B, planned dose levels (dose per infusion) for the dose escalation cohorts are as follows: 72 μg , 110 μg , 160 μg , 240 μg , 360 μg , 480 μg and higher if MTD for Schedule B is not reached. The starting dose for the first cohort on Schedule B will be 72 μg administered as short-term IV infusions daily (QD) during the 14-day cycle 1. The doses administered for the subsequent cohorts will include step-up doses administered in increments of 2 days as described in [Table 4](#). The DLRT may recommend shortening the duration of steps to 1 day or to extend the duration of steps up to 5 days based on the emergent safety, PK and PD data. All subjects will be pre-treated with an 8-mg dose of IV dexamethasone 1 hour prior to the day 1 dose of AMG 673 and prior to each step-up dose of AMG 673 in cycle 1 and prior to all doses in subsequent cycles. Cycle 2 will start immediately after cycle 1 has completed and will consist of 4 AMG 673 infusions: day 1, day 4, day 8, and day 11 of a 14-day cycle at the target dose. Each cycle on Schedule B is planned for 14 days and intervals between cycles up to 2 weeks may be permitted after completion of cycle 2 upon discussion and agreement with Sponsor. Please refer to [Section 6.2.1.1.2](#) for additional information on Schedule B dose schedule, requirements and treatment-free intervals.

Estimation of MTDs

The estimate of the MTD or the estimate of each MTD if step dosing is used will use Bayesian logistic regression model (BLRM) design once a DLT is observed. DLTs experienced by subjects both during and after completing the DLT period will be considered in the BLRM design to account for any late onset toxicity. Schedule A may

result in 2 or more estimates of MTD; MTD1 without step dose, MTD2 with step dose and MTD3 with 2 step doses. Schedule B will utilize the step-up dose schedule described in [Section 6.2.1.1.2](#) to estimate MTD. A final estimate of the MTD and RP2D will be evaluated and confirmed utilizing all DLT evaluable subjects from the dose escalation and the dose expansion cohorts for each schedule.

MTD1 (Schedule A)

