3.4 Replacement of Subjects

Ineligible subjects (ie, subjects who were exposed to investigational product [IP] but post hoc were found to be ineligible) may be replaced. During dose escalation, subjects that are not DLT-evaluable may be replaced (see [Section 6.2.1.3](#) for definition of a DLT-evaluable subject).

For Schedule A, a subject is not DLT-evaluable if he/she drops out earlier than 1 week after the last planned infusion (eg, day 5 or day 19, depending on the cohort) in cycle 1 for reasons other than an AE. All available safety data for subjects who are not DLT-evaluable will still be evaluated and considered in DLRM recommendations. A cycle will be considered complete and the subject will be DLT-evaluable if the subject has received IP treatment as planned (ie, infusions on D1, D5, and D12/D19 if applicable) and has remained on study for at least 1 week after the last dose in cycle 1.

For Schedule B, a subject must complete the 28 day DLT window and is not DLT-evaluable if they have not completed at least 70% of planned target doses in cycle 1 for reasons other than a DLT.

Exception: If a subject has completed treatment as planned but drops out of study earlier than described above due to progressive disease, they will still be considered DLT-evaluable and will not be replaced.

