- PK sampling will occur on day 14-19 of Cycle 1 per [Table 12](#) if the subject will not receive cycle 2 immediately following cycle 1. If subject proceeds to Cycle 2, day 14 (post-dose) through day 19 samples will not be collected and Cycle 2 day 1 (eg day 15 after 1st dose) should be collected per [Table 14](#).

^c Upon recommendation of DLRT and Sponsor agreement, a lower starting dose may be used (eg, 36 µg) for up to the first 2 doses

The DLRT may recommend shortening the duration of steps to 1 day or to extend the duration of steps up to 5 days based on the emergent safety, PK and PD data. If the duration of step-up doses is extended, the duration of a cycle can be extended from 14 days to 28 days. All subjects will be pre-treated with an 8-mg dose of IV dexamethasone 1 hour prior to AMG 673 dose on day 1 and prior to each step-up dose of AMG 673.

Cycle 2 will consist of 4 AMG 673 infusions: day 1, day 4, day 8, and day 11 of a 14-day cycle at the target dose (maximum planned dose received from cycle 1) (see [Table 4](#) below). Cycle 1 schedule may be repeated 1 time before cycle 2 schedule is initiated upon agreement between the Investigator and Sponsor if the patient will likely

Approved

gain additional benefit per Investigator's assessment. If cycle 1 is not repeated, cycle 2 should begin immediately after cycle 1 with no dose free interval.

Table 4. Schedule B – Cycle 2 and Higher Dosing

	Day of Dose (14-Day Cycle)													
	1	2	3	4	5	6	7	8	9	10	11	12	13	14
Cohort 1	72 ^a			72				72			72			
Cohort 2	110 ^a			110				110			110			
Cohort 3	160 ^a			160				160			160			
Cohort 4	240 ^a			240				240			240			
Cohort 5	360 ^a			360				360			360			
Cohort 6	480 ^a			480				480			480			

Unit of dosage = µg

^a Dexamethasone 8 mg IV will be administered 1 hour prior to dose.

Upon recommendation from DLRT, the number of AMG 673 infusions in cycle 2 and higher may be adjusted based on emergent PK, safety, and PD data (eg, weekly [day 1 and day 8 of each cycle]). Subjects will be hospitalized for the whole duration of cycle 1 (ie, a minimum of 15 days), and for at least 48 hours after each AMG 673 administration in cycle 2 and higher. In the absence of any DLTs or SAEs, shorter hospitalization may be considered upon PI recommendation and Medical Monitor agreement after Cycle 2.

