6.2.1.3 Dose-cohort Study Escalation and Stopping Rules, Dose Limiting Toxicities (DLTs)

A DLT will be defined as any of the events described below occurring in a subject during the DLT window, unless clearly attributable to causes other than AMG 673. The DLT window for Schedule A will start on D1 (start of the administration of the first infusion) and last for 14 days for cohorts receiving 2 doses (ie, day 1 and day 5 dose) and for 28 days for subjects receiving 4 doses (ie, days 1,5,12,19). The DLT window for Schedule B will start on D1 (start of the administration of the first infusion) and last for the duration of cycle 1 and 2 (ie, 28 days). The CTCAE (version 4) will be used to assess will be used to assess toxicities/adverse events with the exception of CRS (see [Table 5](#) for grading of CRS).

DLT Evaluation

A subject is not DLT-evaluable if he/she drops out before completion of the DLT window for reasons other than an AE. All available safety data for subjects who are not DLT evaluable will still be evaluated and considered in DLRM recommendations. A subject will be DLT-evaluable if the subject has received the minimum cycle 1 doses planned for the respective cohort defined below:

- Schedule A : 2 doses with a 14-day DLT window, or 4 doses with 28-day DLT window
- Schedule B: completed $\geq 70\%$ of the planned target doses (eg, 10 doses out of a 14-day cycle 1 for cohort 1, at least 9 doses of the 12 planned at target dose cohort 2, etc) with 28-day DLT window

Exception: If a subject has completed treatment as planned but drops out of study before completing the DLT window due to progressive disease, they will still be considered DLT-evaluable and will not be replaced. The DLT window may also be extended retrospectively to assess events starting or persisting outside the window in case the DLT definition is time dependent (eg, in case of neutropenia, see below).

Any adverse event occurring outside the DLT window that is determined by the investigator to be possibly related to the investigational product, which is seen more frequently or is more severe than expected or is persistent despite appropriate

management, can be determined to be a DLT upon unanimous decision by the DLRT after review of the adverse event and all available safety data.

Events to be considered as DLTs and exceptions are listed below:

- Any treatment-related death

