### Dose Escalation Cohorts

Dose Escalation will be conducted in 2 stages: a single subject stage (**Schedule A only**) and a multiple subjects stage. In the single subject cohorts, cohorts 1 and 2, single subjects will be enrolled at dose levels anticipated to be lower than those at which adverse events related to AMG 673 will be observed. Multiple subject cohorts, starting with cohort 3, will enroll and the cohort size will be extended to 3-4 subjects per cohort. The Bayesian logistic regression model (BLRM) design will be used to guide dose escalation. The actual dose selected at each dose decision may be at or below the model's recommended dose as determined by the dose level review team (DLRT) after considering all information. Subjects will be assessed for dose limiting toxicities (DLTs) for the duration of their **first** treatment cycle (ie, 2 weeks from D1 for subjects who receive 2 doses and 4 weeks for subjects who receive 4 **doses in Schedule A and 4 weeks from D1 for subjects in Schedule B**). Subjects who complete the DLT period

may proceed to a higher dose level for the following treatment cycle **after** the next dose level has been deemed safe by **the DLRT, after consultation with Sponsor, if no DLT was reported for that subject** and no  $\geq$  grade 3 adverse event(s), deemed treatment related by the investigator, are reported for that subject.

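### If Schedule B steps are lengthened and cycle 1 becomes 28 days, the DLT window contradicts itself, and on its fixed 28-day reading cohort 6 is cleared after 3 days at target dose instead of 18

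*Protocol*

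**What the plan says.** Schedule B starts every subject at 72 µg daily and, from cohort 2 on, climbs in 2-day steps to the cohort's target dose within a 14-day cycle 1 (Protocol Table 3). Cycle 2 gives four more target doses over 14 days. Section 3.1 makes the step length adjustable: "The DLRT may recommend shortening the duration of steps to 1 day or to extend the duration of steps up to 5 days". Section 6.2.1.1.2 repeats this and adds the longer cycle: "If the duration of step-up doses is extended, the duration of a cycle can be extended from 14 days to 28 days".

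The DLT window is stated in several places:

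- Protocol 6.2.1.3 starts it on D1 and has it "last for the duration of cycle 1 and 2 (ie, 28 days". The evaluability rule in the same section asks for at least 70% of planned target doses with a 28-day window.
- Protocol 3.4: "a subject must complete the 28 day DLT window".
- The synopsis and SAP 3.1: "4 weeks from D1 for subjects in Schedule B".

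Three provisions soften the cut-off. Section 3.1 says "DLTs experienced by subjects both during and after completing the DLT period will be considered in the BLRM design". Under 6.2.1.3, an adverse event outside the window "can be determined to be a DLT upon unanimous decision by the DLRT", and the window can be extended retrospectively for DLTs whose definition depends on time.

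**The concern.** No sentence says what happens to the DLT window when steps and cycle 1 are lengthened. The two halves of the 6.2.1.3 definition then disagree, because a 28-day cycle 1 and a 14-day cycle 2 last 42 days. The other places still point to day 28. On that reading the window closes on the last day of cycle 1 and contains none of cycle 2.

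Time at the target dose is then lost in the highest cohorts, where it matters most. The BLRM (Protocol Appendix H) takes one yes/no outcome per subject at the dose level and gives no weight to time at dose. A subject seen at 480 µg for 3 days without a DLT therefore informs the decision as much as one seen for 18. Steps may be lengthened because of emerging safety data, so observation could shrink after toxicity has appeared, and the error is toward too high a dose. Schedule A has a safeguard that Schedule B lacks: the subject "has remained on study for at least 1 week after the last dose in cycle 1". The DLRT recommendations listed in 10.3.2 do not include changing the window.

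**Working it through.** **Plan's own figures.** 14 + 14 = 28 days. 70% of 14 target doses is 9.8, so 10; 70% of 12 is 8.4, so 9. These match the examples in 6.2.1.3. Table 3 starts 480 µg on D11.

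**Day counts.** For cohort k and step length L, the first target dose falls on day 1 + (k−1)L. Days from then to day 28, inclusive, are 28 − (k−1)L. Infusions with 2-day steps are those in cycle 1 plus 4 in cycle 2. With 5-day steps I assume daily dosing to day 28.

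| Cohort | First target day, L = 2 / 5 | Days at target by day 28, L = 2 / 3 / 4 / 5 | Target infusions by day 28, L = 2 / 5 |
|---|---|---|---|
| 2 | 3 / 6 | 26 / 25 / 24 / 23 | 16 / 23 |
| 3 | 5 / 11 | 24 / 22 / 20 / 18 | 14 / 18 |
| 4 | 7 / 16 | 22 / 19 / 16 / 13 | 12 / 13 |
| 5 | 9 / 21 | 20 / 16 / 12 / 8 | 10 / 8 |
| 6 | 11 / 26 | 18 / 13 / 8 / 3 | 8 / 3 |

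In a 14-day cycle, 5-day steps would give cohorts 4 to 6 no target dose in cycle 1, so the 28-day cycle is needed there.

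**Evaluability in cohort 6 with 5-day steps.** 70% of 3 doses is 2.1, so 3 of 3 are required. A subject who receives them and completes day 28 without a DLT is evaluable.

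**Cycle 1 and 2 reading.** The window lasts 28 + 14 = 42 days, and cohort 6 has days 26 to 42, which is 17 days.

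**Stagger.** Section 3.1 requires at least 7 days between subjects 1 and 2, and at least 96 hours before each later subject. In a cohort of 3, when subject 3 is on day 28, subject 2 is on at least day 28 + 4 = 32 and subject 1 on at least day 32 + 7 = 39. Days at target from day 26 are then at least 3, 7 and 14.

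**Model sensitivity (illustrative).** Assumed prior medians are 0.05 at 72 µg and 0.30 at the reference dose (SAP Appendix C, Section 9 entry), with the two prior tail conditions of Appendix H applied at 72 µg and at the reference dose, and zero correlation. The reference dose is not shown, so 160, 240, 360 and 480 µg were each tried. The assumed history is 0/3 at 72, 110, 160 and 240 µg and 1/6 at 360 µg. Then 2/6 at 480 µg gives P(rate > 0.33) of 0.31 to 0.41, above the 0.25 limit, and the model recommends 360 µg. With 1/6 it is 0.12 to 0.16 and the model recommends 480 µg. One uncounted DLT changes the dose under all four reference doses. In the first cohort at 480 µg, 1/3 gives 360 µg and 0/3 gives 480 µg.

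**Conditional worst case.** Assumed true rates over the six levels are 0.03, 0.06, 0.10, 0.18, 0.30 and 0.50, with each DLT starting 0 to 17 days after the first infusion at the subject's own threshold level. If delays are uniform, the rate seen by day 28 in cohort 6 with 5-day steps is 0.03 + 0.03 + 0.04 + 0.08 × 13/18 + 0.12 × 8/18 + 0.20 × 3/18 = 0.244. If half of delays fall within 3 days (exponential), it is 0.382. With r the rate seen, the chance that 480 µg stays recommended after two cohorts of 3 is (1−r)³ × [(1−r)³ + 3r(1−r)²]:

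- r = 0.50 (planned): 0.125 × 0.500 = 0.062
- r = 0.382: 0.236 × 0.674 = 0.159
- r = 0.244: 0.432 × 0.850 = 0.367

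A 42-day window brings this back to 6–7%. With the minimum stagger and late DLTs counted on a 28-day window, it is 8–12%.

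**Whole trial (2,500 simulated trials per setting, same assumptions).** The MTD is 480 µg in 1.6% of trials as planned against 3.0–5.9% with 5-day steps (reference dose 360 µg), 0.7% against 0.8–2.0% (240 µg), and 0% for both (160 µg). If every late DLT is voted in, the 360 µg figure returns to 1.0–1.7%.

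**The case against.** A reader might infer that the plan simply keeps 28 days. It does not do so cleanly: the 6.2.1.3 definition also refers to both cycles, and that reading gives cohort 6 17 days, close to the planned 18. What can be shown is a contradiction, with the short reading repeated in more places.

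A reader might also take 6% against 16–37% as the size of the problem. Those figures assume that escalation reaches 480 µg, that every subject is cut off at day 28 and that no late DLT ever counts. They also hold the true rate at 50% whatever the step length, although Section 3.1, writing about Schedule A, expects lower initial doses to improve tolerability of later ones. The stagger and the late-DLT provisions shrink the contrast, and the whole-trial effect is small because 480 µg is seldom reached.

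A third tempting reading is that CRS, whose resolution criteria take 5 to 7 days to judge, would be missed. The retrospective extension for time-dependent definitions covers that. It does not cover an ordinary grade 3–5 non-hematologic event that begins after day 28, which needs a unanimous DLRT vote.

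Finally, nothing obliges a decision at day 28. The DLRT reviews data collected after the window, may delay, and may choose a dose below the model's. But nothing prevents a decision then either, and data not yet accrued cannot be reviewed. These points reduce the harm but do not resolve which window applies.

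**Conclusion.** The point stands as an inconsistency that matters in a permitted but optional branch. It needs lengthened steps, mainly of 4 to 5 days, together with escalation to cohort 5 or 6. On the fixed 28-day reading, 5-day steps reduce time at target from 20 to 8 days in cohort 5 and from 18 to 3 days (8 to 3 infusions) in cohort 6, and such a subject is fully evaluable at the escalation decision. On the other reading, cohort 6 has 17 days.

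The day counts follow from the documents, assuming daily dosing continues through a 28-day cycle 1. The model figures rest on assumed rates, delays and reference doses and show direction only. The whole-trial effect is at most a rise from 1.6% to 3.0–5.9% in selecting 480 µg, and it largely disappears if late DLTs are voted in. Priority is modest: worth correcting because the remedy is a wording change that leaves the planned 2-day steps in cohorts 1 to 6 untouched.

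**What to change.** In Protocol 6.2.1.3, define the Schedule B window as running *until day 28 or until 18 days from the first target-dose infusion (counting that day as day 1), whichever is later*. Eighteen days is the least that any cohort in Table 3 has with 2-day steps. Make the synopsis, Section 3.4, the evaluability rule in 6.2.1.3 and SAP 3.1 refer to this window instead of a fixed 28 days or 4 weeks.

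With 5-day steps the window then ends on day 16 + 17 = 33, 21 + 17 = 38 and 26 + 17 = 43 in cohorts 4, 5 and 6, so dose decisions wait 5, 10 and 15 days longer. A few more subjects may become non-evaluable, although 6.2.1.3 already keeps those who completed treatment and left for progressive disease. The 18 days is a choice. Schedule A accepts 10 calendar days from its last planned dose (days 5–14 or 19–28); a 10-day minimum would spare cohort 4, which has 13, while still lengthening cohorts 5 and 6.

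Two further additions should be avoided. Requiring at least four target infusions in cycle 1 would bar a seventh cohort with 2-day steps in a 14-day cycle, which reaches its target on day 13 and has only 2. Fixing a repeated cycle 1 to start on day 15 would be wrong when cycle 1 lasts 28 days.

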For Schedule B, planned dose levels (dose per infusion) for the dose-escalation cohorts are as follows: 72 μg , 110 μg , 160 μg , 240 μg , 360 μg and higher if MTD is not reached. The starting dose for cohort 1 on Schedule B will be 72 μg administered as short-term IV infusions daily (QD) during the 14-day cycle 1 after the 72 μg target dose is found to be relatively safe and tolerable by the DLRT for Schedule A. Cohort 2 and higher will include step-up doses added in each cohort administered in two day increments after the previous step dose up to the target dose in cycle 1 (eg, cohort 2 will start with 72 μg for 2 days followed by 110 μg administered on D3 to D14; cohort 3 will start with 72 μg for 2 days followed by 110 μg on D3 for 2 days followed by 160 μg on D5 to D14, etc). Cycle 2+ doses will be given on days 1, 4, 8 and 11 at the target dose. See [Table 3](#) and [Section 6.2.1.1.2](#) for Schedule B dosing schema by cohort. All subjects will be pre-treated with an 8-mg dose of IV dexamethasone 1 hour prior to the first dose on day 1 and prior to each step-up dose in cycle 1 and prior to all doses in cycle 2 and beyond. There is no treatment free interval between cycle 1 and cycle 2. Beyond cycle 2, a treatment-free interval is allowed for 0 to 14 days depending on treatment response and recovery of blood counts and may be extended as described in [Section 6.2.1.1.1](#) after consultation with Sponsor. Adjustments to dose level, dose frequency and a duration of step dosing may be considered after recommendation of DLRT based on review of available safety, PK, and PD data.

Dose Escalation Cohorts

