6.3 Other Protocol-required Therapies

All other protocol-required and recommended therapies including corticosteroids, that are commercially available are not provided or reimbursed by Amgen (except if required by local regulation). The investigator will be responsible for obtaining supplies of these therapies.

Oxygen: Oxygen administration as a supportive measure is permitted during study treatment.

Hydroxyurea: Hydroxyurea for 7 days at a dose of 1 – 10 g / day is permitted prior to the first cycle of IP treatment for subjects with high WBC (> 15,000 cells/mcL or 15 cells x 10⁹/L). Administration of hydroxyurea after the start of IP must be approved and discussed with the Amgen medical monitor.

Dexamethasone: Premedication with dexamethasone is required prior to day 1 and day 5 of AMG 673 dosing and prior to each step-up dose of AMG 673 to mitigate the risk of CRS in Schedule A. For Schedule B, premedication with dexamethasone is required prior to a dose administered on day 1 and each step-up dose in cycle 1, and prior to every dose in subsequent cycles. When dosed, dexamethasone should be administered as a single IV dose (8 mg) within 1 hour of start of infusion.

Tocilizumab: Tocilizumab may be added to CRS treatment regimen or required to be used in combination with dexamethasone to treat CRS as per protocol [Section 6.6](#).

For administration of tocilizumab or dexamethasone and tocilizumab after occurrence of CRS, follow guidance in [Section 6.6](#). Additional details regarding these protocol-required therapies are provided in the IPIM.

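### For Schedule B from cycle 2 on, Table 4 marks dexamethasone on day 1 only, while four other statements require it before every dose

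*Protocol*

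**What the plan says.** Four statements give the same rule for Schedule B from cycle 2 onward:

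- Protocol Synopsis: dexamethasone is given before the first dose, then "prior to each step-up dose in cycle 1 and prior to all doses in cycle 2 and beyond".
- Protocol 3.1: "prior to each step-up dose of AMG 673 in cycle 1 and prior to all doses in subsequent cycles".
- Protocol 6.3, which lists premedication as required: before the day 1 dose "and each step-up dose in cycle 1, and prior to every dose in subsequent cycles".
- SAP 3.1 repeats the Synopsis rule.

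The dosing section, 6.2.1.1.2, differs in two places:

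- Table 4 (cycle 2 and higher) carries footnote a, "Dexamethasone 8 mg IV will be administered 1 hour prior to dose", on the day 1 cell in each of the six cohort rows. The cells for days 4, 8 and 11 have no mark.
- The premedication sentence calls for "IV dexamethasone 1 hour prior to AMG 673 dose on day 1 and prior to each step-up dose of AMG 673". It says nothing about the remaining doses of cycle 2 and later, which are given at the target dose and so contain no step-up.

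On timing, 6.2.1.1.2 says "If cycle 1 is not repeated, cycle 2 should begin immediately after cycle 1 with no dose free interval". Under 6.2.1.3 the Schedule B DLT window starts on D1 and covers cycles 1 and 2, stated there as 28 days.

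**The concern.** Table 3, the cycle 1 dosing table just before Table 4, uses the same footnote to pick out individual premedicated doses: day 1 and each step-up. A reader coming from Table 3 will take an unmarked cell in Table 4 to mean a dose without dexamethasone, and nothing in 6.2.1.1.2 corrects that reading. A site working from Table 4 would leave out required prophylaxis on days 4, 8 and 11, while a site working from 6.3 would give it.

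Cytokine release syndrome (CRS) is the only identified risk in Protocol Table 1, and dexamethasone is its prophylaxis. CRS also enters the DLT definition in 6.2.1.3: grade 4 events, grade 2 or 3 events that do not resolve in time, and a second separate grade 3 event. Cohorts hold 3 to 4 subjects and the DLT counts feed the BLRM, so premedication inside the DLT window should not depend on which page a site follows.

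**Working it through.** The documents give no figure to reproduce. The check is a comparison of texts and a count.

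**Inputs**

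- Cycle 2 infusion days: 1, 4, 8, 11 (6.2.1.1.2, Table 4)
- Cycle 1 length: 14 days, with no gap before cycle 2 by default (6.2.1.1.2)
- DLT window: 28 days from D1 (6.2.1.3)
- Days marked for dexamethasone in Table 4: day 1 only
- Days requiring it under the Synopsis, 3.1, 6.3 and SAP 3.1: all four
- Dose: 8 mg

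**Default schedule.** Study day = 14 + cycle day.

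| Cycle 2 day | Study day | Within 28 days | Table 4 mark | Required by 6.3 |
|---|---|---|---|---|
| 1 | 15 | yes | yes | yes |
| 4 | 18 | yes | no | yes |
| 8 | 22 | yes | no | yes |
| 11 | 25 | yes | no | yes |

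Three of four cycle 2 infusions are affected, or 3 of 14 + 4 = 18 planned infusions in the window. The difference per subject is 3 × 8 mg = 24 mg, the same in every cohort.

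**Permitted variations**

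- The DLRT may change the number of infusions: "the number of AMG 673 infusions in cycle 2 and higher may be adjusted based on emergent PK, safety, and PD data". With the weekly example (days 1 and 8), the study days are 15 and 22. One of two is affected, a difference of 8 mg.
- If cycle 1 is repeated, or extended to 28 days, cycle 2 falls on study days 29, 32, 36 and 39. None is within 28 days.

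**Exposure already received without dexamethasone.** This bears on how much the omission could matter. Table 3 marks exactly one target dose per cohort in cycle 1.

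| Cohort | Target doses in cycle 1 | Marked | Without dexamethasone |
|---|---|---|---|
| 1 | 14 | 1 | 13 |
| 2 | 12 | 1 | 11 |
| 3 | 10 | 1 | 9 |
| 4 | 8 | 1 | 7 |
| 5 | 6 | 1 | 5 |
| 6 | 4 | 1 | 3 |

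**Could the marks have been lost when the PDF was read?** This is unlikely. The pattern is the same in all six rows of Table 4, the marks in Table 3 survived, and the sentence in 6.2.1.1.2 also lacks the later-cycle rule.

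**The case against.** The strongest reply is that 6.3 governs premedication and states the rule outright, with the Synopsis and 3.1 in agreement. A missing superscript does not override an explicit requirement, and no sentence forbids dexamethasone on days 4, 8 or 11. Section 6.3 also refers sites to the IPIM, which is not available here and may settle the matter in practice. All of this stands. It makes the intent clear, but the dosing table still omits it.

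A second reply is that the 6.2.1.1.2 sentence closes a paragraph about cycle 1 step lengths and is correct for cycle 1. That is a fair reading. The paragraph that follows, on cycle 2, still gives no premedication rule, so the section as a whole lacks one.

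A third reply is that the consequence is small. Subjects have by then had 3 to 13 target doses without dexamethasone by design. Section 6.6 expects CRS after the first infusion and after dose steps, and these infusions are neither. Cycle 2 requires at least 48 hours in hospital after each dose, and under the CRS criteria a single grade 2 or 3 event that resolves quickly would generally not be a DLT. These points limit the likely effect on the DLT rate. They do not remove the contradiction about a required safety measure.

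Finally, the count of zero when cycle 1 is extended depends on reading the window as a fixed 28 days. The text says the window will "last for the duration of cycle 1 and 2 (ie, 28 days", and those two descriptions part company if cycle 1 is longer than 14 days. On the reading by cycles, an extended cycle 1 would leave the cycle 2 infusions inside the window.

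**Conclusion.** The point holds and should be fixed. Table 4 omits a premedication requirement that four other statements make, and the section around it does not supply the missing rule. On the default schedule (14-day cycle 1, not repeated, four cycle 2 infusions), 3 of 4 cycle 2 infusions in the DLT window are affected, a difference of 24 mg per subject. It is 1 of 2 under weekly dosing, and 0 within 28 days if cycle 1 is repeated or extended to 28 days. The counts of cycle 1 doses without dexamethasone assume Table 3 as printed; other step lengths would change them. The shift in the DLT rate cannot be estimated from the documents and is probably small. What the IPIM tells sites is not known.

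**What to change.** Add footnote a to days 4, 8 and 11 in Table 4 for all six cohorts: 6 × 3 = 18 cells. In 6.2.1.1.2, extend the premedication sentence so that it ends as the Synopsis does, "prior to each step-up dose in cycle 1 and prior to all doses in cycle 2 and beyond", which also matches 6.3. If the sponsor prefers to keep that paragraph to cycle 1, the same clause can go in the next paragraph, which introduces Table 4.

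The cost is a protocol clarification: footnote marks in one table and one added clause. It needs no new data or procedures. After the change, 0 of 4 cycle 2 infusions carry inconsistent instructions.
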